#### 6.5.4 Special Precautions

Based on nonclinical safety findings, the main target organs of toxicity are lymphatic and hematopoietic systems, pancreas, kidneys, lung, liver, stomach, and intestine. In association with the decrease in B-lymphocytes, infections may be a potential risk; therefore, subjects receiving M3541 should be monitored for adverse effects of lymphatic and hematopoietic systems, gastrointestinal system (including liver and pancreas), kidneys, and respiratory system should be considered. Further, hematological and clinical chemistry monitoring should include WBC count and monitoring of liver, renal, and pancreas enzymes.

# 6.5.5 Management of Specific Adverse Events or Adverse Drug Reactions

No specific AEs or ADRs of particular concern have been identified. The Investigator should use clinical judgment and follow the guidelines in Table 7 the management of AEs / ADRs.

# 6.6 Packaging and Labeling of the Investigational Medicinal Product

The M3541 film-coated tablets will be ready for oral use. The tablets will be packed into high density polyethylene bottles (10 tablets per bottle) "child proof system" bottles with desiccant.

All IMPs will be packaged and labeled in accordance with all applicable regulatory requirements and Good Manufacturing Practice Guidelines.

# 6.7 Preparation, Handling, CC of the Investigational Medicinal Product

Do not freeze. Detailed information can be found in the pharmacy

# manual.

# 6.8 Investigational Medicinal Product Accountability

The Investigator is responsible for ensuring IMP accountability, including reconciliation of drugs and maintenance of records.

• Upon receipt of IMP, the responsible person will check for accurate delivery and acknowledge receipt by signing and / or initialing and dating the appropriate documentation and returning it to the location specified. A copy will be archived for the Investigator Site File.

- IMP dispensing will be recorded on the appropriate drug accountability forms so that accurate records will be available for verification at each monitoring visit.
- Study site IMP accountability records will include the following:
  - Confirmation of IMP receipt, in good condition and in the defined temperature range.
  - The inventory of IMP provided for the clinical study and prepared at the site.
  - The use of each dose by each subject.
  - The disposition (including return, if applicable) of any unused IMP.
  - Dates, quantities, batch numbers, expiry dates, and the individual subject study numbers.

The Investigator site should maintain records that adequately document that subjects were provided the doses specified in this protocol and all IMPs provided were fully reconciled.

The Sponsor's Monitor will periodically collect and review the IMP accountability forms and where applicable, will check all returns (both unused and used containers) before arranging for their return or authorizing their destruction by the study site.

At the conclusion or termination of this study, study site personnel and the Clinical Study Monitor will conduct a final product supply inventory on the Investigational Drug Accountability Forms and all unused containers will be destroyed. Instructions for destruction of product will be provided to the site. The Clinical Study Monitor will be supplied with a copy for filing of the Investigational Drug Accountability Forms. This documentation must contain a record of clinical supplies used, unused, and destroyed and shall include information on:

- All administered units
- All unused units
- All destroyed units (during the study)
- All destroyed units at the end of the study
- Date of destruction(s)
- Name and signature of the Investigator / pharmacist.

It must be ensured at each study site that the IMP is not used

- · After the expiry date, and
- After the retest date unless the IMP is reanalyzed and its retest date extended.

This is to be closely monitored by the Clinical Study Monitor.

# Document No. CC

# 6.9 Assessment of Investigational Medicinal Product Compliance

As M3541 is administered at the clinic, no special compliance monitoring is required; however, the exact time of M3541 administration and start of RT should be recorded appropriately in the eCRF.

#### 6.10 Blinding

Not applicable.

# 6.11 Emergency Unblinding

Not applicable.

# 6.12 Treatment of Overdose

An overdose is defined as any dose greater than the highest daily dose included in a clinical study protocol or planned for an individual subject enrolled in the study. Even if it does not meet other criteria for an SAE, any overdose must be recorded in the study medication section of the eCRF and reported to Drug Safety in an expedited manner using the SAE Report Form, and following the procedure in Section 7.4.1.4.

There is no established treatment for overdose with M3541. The Investigator should use clinical judgment to manage any overdose and should be guided by the nature of the presenting symptoms and standard evaluation results, and use standard treatment for those observations.

# 6.13 Medical Care of Subjects after End of Study

After a subject has completed the study or has withdrawn early usual treatment will be administered, if required, in accordance with the study site's standard of care and generally accepted medical practice and depending on the subject's individual medical needs.

Upon withdrawal from the study, subjects may receive whatever care they and their physicians agree upon. Subjects will be followed for survival as specified in Section 7.1.4.

# 7 Study Procedures and Assessments

#### 7.1 Schedule of Assessments

Schedules of Assessments are provided in Table 1 through Table 6.

# 7.1.1 Screening and Baseline Procedures and Assessments

During the Screening period and before any study-related investigations and assessments are started that are not part of routine medical care for the subject, the subject will be asked to sign the relevant Informed Consent Forms (ICFs) as described in Section 9.2.

The washout period for prior anticancer treatment is defined in Section 6.5.2. Major surgery is not permitted within 28 days before the start of study treatment (Section 6.5.3). Hematology and chemistry laboratory samples must be drawn and reviewed within 24 hours prior to first dose administration.

The subjects' information that will be documented during Screening includes the demographic information (birth date, sex, ethnicity, and race) and the complete medical history, including the history of the tumor disease and prior anticancer therapies, previous medications (prior 30 days to signing of ICF), concomitant medications, and baseline medical condition (the information of concomitant medications and AEs will be monitored throughout the study treatment period). Moreover, an Emergency Medical Support card will be handed out at the baseline assessments visit.

All subjects will be asked to complete the Brief Pain Inventory – Short Form (BPI-SF) at Screening prior to other study-related assessments. If a subject has no pain in an area to be irradiated as part of the experimental treatment (M3541 + RT), the subject should mark "0" in all pain scales and activity scales. For subjects with cancer pain from lesions to be irradiated as part of the experimental treatment, any pain medication should be documented (name, dose, frequency, including if used on an "as needed" basis) on the appropriate eCRF page.

During Screening, subjects will undergo a complete physical examination, dermatological assessments (assessments for skin lesions or rash with biopsy of suspicious lesions), vital signs assessments (body temperature, respiration rate, pulse, blood pressure), body weight and height (height only at Screening), 12-lead electrocardiogram (ECG), determination of the ECOG PS (Appendix I) and laboratory assessments, including hematology / coagulation, serum chemistry, and urinalysis as outlined in Table 1, Table 2, or Table 3 as appropriate.

During Screening, a serum  $\beta$ -human chorionic gonadotropin ( $\beta$ -HCG) pregnancy test will be performed for females of child bearing potential (see detailed information in Appendix III).

Subjects must be tested for HBV and HCV at Screening (as these conditions are study entry exclusion criteria) unless test results obtained within 3 months prior to Screening are available. Screening for HIV will be performed according to local practice and local regulatory guidance.

Although not mandatory, all efforts should be made by the study site to request a historical tissue sample before the first dose of study drug (see Section 7.6).

The tumor evaluation (type / staging, etc) should be performed at Screening (see Section 7.2.5 for details). Bone scans should be performed as clinically indicated. A brain CT / MRI scan (either, contrast preferred) is required at Screening if not performed within the previous 6 weeks.

# 7.1.2 Treatment Period

The treatment period consists of 10 FDs (FD 1 to FD 10 over a 2-calendar week period) of palliative RT (5 FDs per week with FD 1 on a Monday and with the Saturday and Sunday between FD 5 and FD 6 as an RT holiday). M3541 is administered either on a once per FD schedule

(Table 1), or on an intermittent schedule of thrice weekly (Table 2) or twice weekly (Table 3) schedules, with M3541 always administered on RT FDs. In case the Investigator inserts RT holidays (interruption due to toxicity, see Section 6.2.1), M3541 treatment should be suspended and should be restarted with RT at the next first RT day for which M3541 is scheduled to be given.

All effort should be made to complete RT with 10 FDs if possible. Subjects will be asked to visit the investigational site according to the Schedule of Assessments (see Table 1, Table 2, or Table 3 as appropriate) in order to receive M3541 and RT and for study assessments to be performed.

The following instructions should be followed:

- All subjects will be asked to complete the BPI-SF on FD 1 prior to other study-related assessments. Subjects with cancer pain from lesions to be irradiated as part of the experimental treatment (M3541 + RT) on FD 1 will be asked to complete the BPI-SF on each subsequent FD prior to any other study-related procedures. The subject should only rate pain and interference with daily activity as they relate to areas being irradiated as part of the experimental treatment. The Investigator must also ensure any new pain medication or change in ongoing pain medication (drug, dose, frequency, including any change in "as needed" dosing) is reported on the appropriate concomitant medications eCRF page
- Subjects should be instructed to consume a light breakfast prior to arriving at the clinic for M3541dose administration
- On M3541 treatment days, M3541 should be given at the study site 1 hour and 45 minutes (± 60 minutes) before RT is started
- On M3541 treatment days when samples for PK and pharmacodynamics determination are scheduled, M3541 should not be given until the predose PK and pharmacodynamics (as appropriate) collection has been completed (see Table 4, Table 5, or Table 6 as appropriate)
- ECGs will be acquired according to Table 4, Table 5, or Table 6 as appropriate and should be collected prior to any associated PK and pharmacodynamic blood sampling. The ECG should be obtained using a Holter recorder.

# 7.1.3 Dose-limiting Toxicity Evaluation Period

The DLT evaluation period will be 4 weeks in duration, including the 2-week treatment period (including a 2-day M3541 / RT holiday after FD 5) plus a 2-week DLT follow-up period that starts on the day after the last administration of M3541 / RT (see Figure 1). After the M3541 / RT treatment period, subjects will return to the clinic on PTD 15 (+ 2 days) for assessments (including the BPI-SF as applicable) as outlined in Table 1. The DLT evaluation period could exceed the 4-week period only if M3541 / RT has been interrupted and given over a period exceeding 2 weeks.

Subjects with ongoing AEs should present to the clinic throughout the DLT follow-up period as appropriate and instructed by the Investigator (see Section 6.5 and subsections for allowed and

prohibited medications). It is expected that the Investigator will follow his / her subjects and will ask subjects to come in to the clinic (and document) when AEs are known to happen. In absence of any new or major toxicity / AE during the DLT follow-up period, the subject need only be seen on PTD 15 (+ 2 days) and PTD 22 ( $\pm$  2 days).

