- b. FD 1 is the first dose of M3541 and first fraction of RT. Planning of the RT will follow institutional guidelines and will start on a Monday (with the first Saturday and Sunday as a M3541 / RT holiday). In cohorts where required, subjects will be asked to stay overnight in a supervised environment on FD 1 unless the PK sampling and ECG assessment at 8 and 12 hours postdose can be completed otherwise. FD 10 is the last administration of M3541 / RT and the DLT follow-up period will start on the following day (PTD 1). In case of premature withdrawal from the study during the treatment period, the assessments scheduled for the visit on FD 10 should be performed. In such cases, this visit will be considered the EoS visit. If FD 10 is on a Friday then safety laboratory assessments and urinalysis (as required) must be done on FD 9.

- c. The 2-week DLT follow-up period (PTDs 1 through 14) starts on the day after the last administration of M3541 / RT. With the treatment period starting on a Monday, PTD 15 will land on a Saturday. The PTD 15 visit has a + 2 days visit window, thus subjects should present to the clinic on the following Monday for the PTD 15 DLT follow-up visit. PTD 22 will also land on a Saturday. The PTD 22 visit has a ± 2 days visit window, thus subjects should present to the clinic for this safety assessment on either the preceding Thursday/Friday (PTDs 20/21) or the following Monday (PTD 24). Subjects with ongoing AEs should present to the clinic throughout the DLT follow-up period as appropriate and instructed by the Investigator. See Section 6.5 and subsections for allowed and prohibited medications during the DLT period.
- d. Subjects must meet all inclusion criteria and not any exclusion criteria prior to enrollment. Hepatitis B and C results obtained within 3 months prior to screening are still valid for the purpose of this study. In the case of new clinical laboratory abnormalities detected prior to the first dose, the eligibility of the subject should be reconsidered.

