# 5.1.1 Dose-limiting Toxicity

For this study, a DLT is defined as any of the following AEs that occur during the DLT evaluation period (except those that are clearly and incontrovertibly due to disease progression or extraneous causes), with severity graded according to the National Cancer Institute (NCI) Common Terminology Criteria for Adverse Events, Version 4.03 (CTCAE V4.03):

- Grade  $\geq$  3 non-hematologic toxicity, except:
  - $\circ$  Nausea, vomiting and / or diarrhea lasting  $\leq$  3 days in the once per FD and twice weekly schedules or 2 days in the thrice weekly schedule that can be medically managed
  - Worsening of pre-existing tumor pain associated with tumor lesions for which the subject is irradiated in the context of this study
- Evidence of treatment-related hepatocellular injury for > 3 days in the once per FD and twice weekly schedules and 2 days in the thrice weekly schedule, such as ≥ 5 × the upper limit of normal (ULN) of alanine aminotransferase (ALT) or aspartate aminotransferase (AST) and without any other apparent clinical causality
- Any occurrence of Hy's law (defined as aminotransferases > 3 × ULN, alkaline phosphatase < 2 × ULN, total bilirubin ≥ 2 × ULN, with no other reason to account for these abnormalities)
- Febrile neutropenia or Grade 4 neutropenia lasting for > 5 days, Grade 4 thrombocytopenia or any requirement for platelet transfusion (as defined by Grade 4 thrombocytopenia lasting for > 5 days or Grade ≥ 3 thrombocytopenia with bleeding), Grade 4 anemia that is unexplained by the underlying disease
- Any toxicity related to study treatment that causes the subject to interrupt treatment (defined as having to delay the next scheduled M3541 administration) for:
  - $\circ \geq 4$  FDs in the once per FD dosing schedule.
  - $\circ$  > 1 FD in the thrice weekly schedule
  - not to be able to be treated within 24 hours of the scheduled treatment time in the twice weekly schedule
- A related treatment-emergent adverse event (TEAE) that in the opinion of the SMC is of potential clinical significance such that further dose escalation would expose subjects to unacceptable risk.

Information on DLTs will be sent by the Sponsor or delegate to the SMC core members within 1 working day of the receipt of documented information.

Document No. CC Object No. CC

Dose escalation of M3541 will start from 50 mg orally once per FD until 1 of the following stopping rules apply:

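### Once-per-FD schedule: no safety haematology or chemistry is scheduled from FD 9 to the PTD 15 (+2) visit, so a silent laboratory-defined DLT that resolves in between may go unseen

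*Protocol*

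**What the plan says.** For the once-per-FD schedule, Table 1 footnote c sets the window: "The 2-week DLT follow-up period (PTDs 1 through 14) starts on the day after the last administration of M3541 / RT". Footnote b moves the last on-treatment bloods forward: "If FD 10 is on a Friday then safety laboratory assessments and urinalysis (as required) must be done on FD 9". With Monday starts FD 10 is a Friday, so this is the normal case. Footnote c notes that PTD 15 is then a Saturday: "thus subjects should present to the clinic on the following Monday for the PTD 15 DLT follow-up visit".

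After treatment, Table 1 marks haematology and chemistry only at PTD 15 (+2), PTD 22 and PTD 30. The rows are complete in the tracked copy in Appendix V. Section 7.1.3 says of the follow-up: "In absence of any new or major toxicity / AE during the DLT follow-up period, the subject need only be seen on PTD 15", together with PTD 22. Extra visits depend on known events: "Subjects with ongoing AEs should present to the clinic throughout the DLT follow-up period as appropriate and instructed by the Investigator".

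The DLT definition (Section 5.1.1) includes "Febrile neutropenia or Grade 4 neutropenia lasting for > 5 days, Grade 4 thrombocytopenia or any requirement for platelet transfusion", ALT or AST at 5 x ULN or more for over 3 days, and any Hy's law case. Section 6.5.4 states that "the main target organs of toxicity are lymphatic and hematopoietic systems, pancreas, kidneys, lung, liver, stomach, and intestine".

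A subject without a DLT is evaluable with at least 80% of each treatment plus a safety assessment on PTD 15 (+2) (Protocol Section 8.4), or one safety result on or after the end of the period (SAP Section 8.2). Neither asks for a laboratory result from PTD 1-14.

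**The concern.** DLT occurrence over treatment plus follow-up is the primary endpoint, and it is the only outcome entered in the dose-escalation model. For laboratory-defined DLTs the follow-up half has no scheduled measurement until after it closes. An asymptomatic cytopenia or transaminase rise becomes known only from a blood test, so a rule that calls in subjects with known AEs does not reach it. Exposure also continues into this stretch. Section 3.1.5 puts the half-life above 48 hours, and five half-lives of 2 days reach PTD 10.

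An event that comes and goes unsampled enters the model as a non-DLT. That lowers the estimated DLT rate and raises the dose the model will accept. It also leaves an unmonitored interval in a first-in-human study for organs that the protocol itself names as targets.

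**Working it through.** **Calendar.** Set FD 1 = Monday = day 1.

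- FD 9 = day 11 (Thursday); FD 10 = day 12 (Friday).
- PTD k = day 12 + k. PTD 14 = day 26, PTD 15 = day 27 (Saturday), PTD 17 = day 29 (Monday), PTD 22 = day 34 (Saturday), PTD 24 = day 36 (Monday). These reproduce every weekday stated in Table 1 footnote c.
- Gap from the FD 9 draw: 27 - 11 = 16 days, or 29 - 11 = 18 days for the Monday visit.
- The SAP ends the DLT period 14 days after the last administration, on day 26. The part after treatment is 14/26 = 54% of it.

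**Which events escape.** An event of D whole days starting on PTD o covers PTD o to o + D - 1. A draw on PTD x sees it if o <= x <= o + D - 1. With only a closing draw on PTD x, the unseen onsets among PTD 1-14 are those with o <= x - D.

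| Event | Closing draw PTD 15 | Closing draw PTD 17 | Draws PTD 10 and PTD 17 |
|---|---|---|---|
| 4 days (shortest whole-day event > 3 days) | 15 - 4 = 11 of 14 | 17 - 4 = 13 of 14 | 9 of 14 (o = 1-6, 11-13) |
| 6 days (shortest whole-day event > 5 days) | 15 - 6 = 9 of 14 | 17 - 6 = 11 of 14 | 5 of 14 (o = 1-4, 11) |
| 10 days | 15 - 10 = 5 of 14 | 17 - 10 = 7 of 14 | 0 of 14 |

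A 6-day event lies wholly inside PTD 1-14 for nine onset days (o = 1-9). No scheduled draw sees any of the nine. With a PTD 10 draw, four of the nine remain unseen.

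**Duration.** An abnormality first found on PTD 15-17 cannot be shown from one draw to have lasted more than 3 or 5 days. The next scheduled draw is PTD 22 (+/- 2).

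**Where the 240-hour attendance falls.** 240 hours after FD 10 is day 12 + 10 = 22, which is PTD 10 (PTD 9-11 with the 24-hour window). Table 4 footnote d calls it PTD 8. That label fits numbering in which PTD 1 is the third day after FD 10 (PTD = day - 14, so 22 - 14 = 8), which Tables 2 and 3 still use. Footnote d marks only the 72-hour PK sample as optional. Section 7.1.3 does not mention the 240-hour attendance.

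**What one unseen event can do to the model (illustration).** Inputs: the stated prior means and SDs, taken as independent normals; 0/3 at 50 mg and 0/4 at 100 mg (Section 3.1.5, assuming all seven are evaluable); then a hypothetical 0/3 or 1/3 at 200 mg. The reference dose is not given, so five values were tried. P(DLT rate > 35%) at 300 mg:

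| Reference dose (mg) | 0/3 | 1/3 | Crosses 25% |
|---|---|---|---|
| 100 | 0.19 | 0.47 | yes |
| 200 | 0.43 | 0.65 | no, above in both |
| 300 | 0.22 | 0.35 | yes |
| 500 | 0.02 | 0.13 | no |
| 800 | 0.01 | 0.07 | no |

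At 200 mg itself the limit is crossed for reference doses 100 (0.09 to 0.32) and 200 (0.08 to 0.26).

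**The case against.** The case for leaving the schedule alone has substance.

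- Treatment is well sampled: Table 1 gives six on-treatment draws in two weeks. The closing visit carries full bloods, and PTD 22 and PTD 30 repeat them.
- To escape, an event must be silent, start after FD 9 and resolve before PTD 15-17. A long Grade 4 cytopenia would often leave a lower-grade trace at one end.
- The SAP (Section 9) includes unscheduled results. Section 7.4.4 has abnormal findings reassessed, and Section 7.1.3 expects investigators to call subjects in when AEs are known.
- The model is advisory. The SMC also weighs AEs, laboratory and PK data, may itself declare a related TEAE a DLT, and reviews findings from weekend-postponed visits.
- Section 3.1.5 reports eight subjects dosed, no DLT, and at most Grade 1 treatment-related toxicity.
- Amendment 4 shortened the gap. With the PTD 22 visit on the older numbering, the next bloods were on day 14 + 22 = 36, or 25 days after FD 9.

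Most of this stands, and it limits the point. A reader might infer that any laboratory DLT arising after treatment is lost. The documents do not support that, because events still present at PTD 15-17, symptomatic events and unscheduled results would be captured. What is not answered is the silent, transient event. None of these provisions schedules a blood test on PTD 1-14, and the evaluability rules do not require one.

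**Conclusion.** The gap is real: 16 to 18 days, covering all 14 follow-up days. A clinically silent laboratory-defined DLT confined to it may be missed by the scheduled draws, and the subject would be counted as DLT-free. The direction of any bias is a lower DLT rate and a higher MTD.

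A reader might go further and conclude that the MTD is materially biased. The documents do not show this. They give no rate for silent transient events, so the bias cannot be sized. The onset-day fractions describe the schedule's coverage under uniform onset and whole-day durations, and are not probabilities that a DLT is missed. The model illustration depends on an unstated reference dose; at 300 mg the overdose limit is crossed for two of the five values tried.

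The point is limited to the once-per-FD schedule. SAP Section 7 says the intermittent schedules were never explored. I rate it a recommended cheap improvement and not a must-fix.

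**What to change.** 1. Reconcile the day labels first. Table 4 footnote d puts 240 hours at PTD 8, whereas Amendment 4 numbering gives PTD 10. Section 7.1.3 asks for no attendance before PTD 15, although Table 4 schedules the 240-hour one.
2. Add local haematology and serum chemistry to that 240-hour (+/- 24 h) PK/ECG attendance. Show the draw in the DLT follow-up column of Table 1 and in Section 7.1.3.
3. Provide for repeat sampling when a value reaches a DLT grade, so that the > 3-day and > 5-day criteria can be judged.

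The cost is a small extra blood volume at an attendance where PK blood is already drawn, the local laboratory charge, and the wording changes. One draw narrows the gap without closing it. With the closing visit on PTD 17, unseen onset days fall from 11 to 5 of 14 for a 6-day event, and from 13 to 9 of 14 for a 4-day event.
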